- A subsequent double blind active treatment period, during which subjects can receive multiple active IMP retreatment administrations of either 600 U or 800 U Dysport®.

Duration of subject participation

104 weeks (24 months) to 116 weeks depending on the timing of final IMP administration.

Screening

Screening period will last for up to 30 days (but can be extended in certain circumstances, see Section 5.2.1), during which time informed consent will be obtained and eligibility for study participation will be assessed. Subjects will complete a 7-day bladder diary, urodynamic assessment, patient-reported outcome questionnaires and have blood and urine samples taken.

Randomisation/treatment

The Treatment Visit (Day 1) should occur up to 14 days after screening period (but can be extended where a UTI has occurred, see Section 5.2.3). At the Treatment Visit (Day 1), subjects who meet all the eligibility criteria will be randomised (in a 2:2:1:1 ratio) to one of four treatment sequences:

Sequence	Subjects	Treatment 1	Subsequent retreatment(s)
1	110 subjects	600 U Dysport®	600 U Dysport®
2	110 subjects	800 U Dysport®	800 U Dysport®
3	55 subjects	Placebo	600 U Dysport®
4	55 subjects	Placebo	800 U Dysport®

During analysis of study Treatment 1, the two placebo containing sequences will be pooled into a single arm.

Randomisation will be stratified by aetiology of NDO (SCI or MS) and also by previous intradetrusor botulinum toxin type A (BTX-A) usage (BTX-A naive vs. BTX-A non-naive in the bladder).

IMP administration may be performed using local anaesthesia (if required) or a short-duration general anaesthesia (if required), and will consist of 30 cystoscopically placed injections (0.5 mL per injection point) of the IMP evenly distributed throughout the bladder (avoiding the trigone). CCI

Follow-up (after the first IMP administration):

- Week 1 (Day 8) (telephone)
- Week 2 (Day 15) (clinic visit)
- Week 4 (Day 29) (telephone)
- Week 6 (Day 43) (clinic visit; primary timepoint)
- Week 12 (Day 85) (clinic visit)
- Every 12 weeks (telephone visits; until retreatment received or end of study (EOS) at Week 104 116).

Details of the procedures performed at each visit following the first treatment are shown in [Table 2](#).

Retreatment assessment

A subject may request retreatment at any time ≥ 12 weeks after their most recent study treatment.

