3.3 Randomisation and Blinding

3.3.1 Randomisation

The randomisation will be done in a 2:2:1:1 ratio to one of four treatment sequences:

Sequence	Subjects	Treatment 1	Subsequent retreatment(s)
1	110 subjects	600 U Dysport®	600 U Dysport®
2	110 subjects	800 U Dysport®	800 U Dysport®
3	55 subjects	Placebo	600 U Dysport®
4	55 subjects	Placebo	800 U Dysport®

During analysis of study Treatment 1, the two placebo containing sequences will be pooled into a single arm.

Randomisation will be stratified by:

- 1) Aetiology of NDO (SCI or MS)
- 2) Previous intradetrusor BTX-A usage for UI (BTX-A naive vs. BTX-A non-naive in the bladder).

The sponsor's randomisation manager who is a statistician independent from the study, will prepare three lists which will be performed in blocks and will be based on computer-generated randomisation lists:

- List A: a list of randomisation numbers, which will be produced in an unbalanced ratio 2:2:1:1 for the four treatment sequences and which will be stratified by aetiology and prior intradetrusor BTX-A usage for UI
- List B: a list of double blind treatment numbers, which will be specified on the treatment packs to be dispatched to the sites in order to dispense the drug in Treatment 1 and possibly for subsequent retreatments. It will be produced in a balanced ratio 1:1:1 for 600 U Dysport[®], 800 U Dysport[®] and placebo
- List C: a list of double blind treatment numbers, which will be specified on the treatment packs to be dispatched to the sites in order to dispense the drug for retreatments (but not in Treatment 1). It will be produced in a balanced ratio 1:1 for 600 U Dysport[®] and 800 U Dysport[®].

The assignment of randomisation and treatment numbers at drug dispensing (at Treatment 1 and subsequent retreatments) will be managed by interactive response technology (IRT).

After eligibility is confirmed at the Treatment Visit (Day 1), subjects will be assigned by IRT to a randomisation number and to the associated treatment sequence, in a sequential order within each site (and within each level of strata). A treatment number will also be allocated by the IRT each time the drug is dispensed, according to the allocated treatment sequence. The IRT will also manage all the logistical aspects of treatments and associated incidents (e.g. drug supplies, replacement of lost, damaged, quarantined, expiring and expired kits).

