3.5 Stopping Rules and Discontinuation Criteria

During the conduct of the study, SAEs will be reviewed (see [Section 8.1.4](#)) as they are reported from the study sites to identify safety concerns.

The sponsor may terminate this study at any time. Reasons for termination include but are not limited to:

- The incidence or severity of AEs in this or other studies point to a potential health hazard for study subjects
- Insufficient subject enrolment
- Any information becoming available that substantially changes the expected benefit/risk profile of the study treatments.

A subject may discontinue participation in the study at any time for any reason (e.g. lack of efficacy, withdrawal of consent, AE) (see [Section 4.4](#)).

The investigator and/or sponsor can withdraw a subject from the study at any time for any reason (e.g. protocol deviation as defined in [Section 11.1.2](#), noncompliance with the protocol conditions or AE).

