7.6.5 Hierarchical Analysis of Secondary Efficacy Endpoints

As specified in Section 7.6.12, a hierarchical analysis will be performed in the order listed for the following six secondary efficacy endpoints at Week 6 after the first IMP administration:

- 1) Mean change from study Baseline in the MCC
- 2) Mean change from study Baseline in the MDP during storage
- 3) Mean change from study Baseline in the Vol@1stIDC
- 4) Proportion of subjects with no episodes of UI (i.e. continence is achieved)
- 5) Proportion of subjects with no IDCs during storage
- 6) Mean change from study Baseline in the I-QoL total summary score

The Derivation rules are specified in Section 3.2 and Appendix II.

For 1), 2) and 3), an ANCOVA model will be fitted using the “mean change” endpoint, as the response variable to obtain the p-value of treatment groups. The model will be the same as the sensitivity analyses for the primary efficacy endpoint in 7.6.4.2. The LSMEANS of the mean change from study baseline at Week 6 in each group with standard error, the difference of mean between the two treatment groups, the 95% CI of the difference and the p-value for treatment group will be presented.

For 4), a logistic generalised linear mixed model (GLMM) for repeated measures will be fitted for UI responses using repeated measurements at Week 2, Week 6, and Week 12. The “proportion of subjects with no episodes of UI” will be analysed as a response variable, the model will include treatment group, stratification variables, study baseline value, visit (week 2, week 6 and week 12), study baseline*visit and treatment*visit interactions as fixed effect. The study baseline value will be weekly number of UI episodes. The logistic GLMM is fitted using the logit link and the binomial distribution. Odds ratios, 95% CIs of odds ratio, and p-values for treatment group comparisons at each visit (week 2, week 6 and week 12) will be presented.

The SAS codes of GLMM for reference are below.

```
CCI
[Redacted SAS code]
```

CCI
[Redacted]
[Redacted]
[Redacted]

For 5), a logistic regression model will be performed with “proportion of subjects” as the response variable. The model will include treatment group, and stratification variables.

Odds ratio, 95% CI of odds ratio, and p-value will be presented.

The SAS codes of logistic regression for reference are below.

CCI
[Redacted]
[Redacted]
[Redacted]
[Redacted]
[Redacted]
[Redacted]
[Redacted]
[Redacted]

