7.6.6.4 Retreatment intervals

For both the DBPC Cycle and by the Dysport Cycles, summary statistics will be displayed for time between treatments received, time to request and time to eligibility for retreatment. For the DBPC Cycle the number and percentage of patients receiving retreatment: \geq Week 12 to $<$ Week 16, \geq Week 16 to $<$ Week 20 weeks and then every 4 weeks will be presented.

The following formal statistics will be performed only for the time between treatments received endpoint. For both the DBPC Cycle and by the Dysport Cycles, median number of days together with the 25th and 75th percentiles and their 95% CI will be determined based on the Kaplan-Meier method. Patients with no retreatment will be censored at the last visit. The survival curves will be presented by treatment group as well.

For the DBPC and Dysport treatment cycles, the log-rank tests will be performed to compare survival curves between treatment groups, by providing p-values.

The SAS codes of survival analysis for reference are below.

CCI
[Redacted SAS code]

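### Duration of effect (SAP 7.6.6.4): the readable log-rank text does not say whether the test is stratified and gives no between-arm estimate, and subjects who leave for lack of efficacy are censored with no sensitivity analysis

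*SAP*

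**What the plan says.** Protocol 3.2.2.1 lists three measures of duration of effect: time to request retreatment, time to eligibility, and time between treatments. SAP 7.6.6.4 summarises all three and then narrows the inference: "The following formal statistics will be performed only for the time between treatments received endpoint". For that endpoint it plans Kaplan-Meier medians and quartiles with 95% CIs, survival curves by treatment group, and a test: "the log-rank tests will be performed to compare survival curves between treatment groups, by providing p-values".

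The censoring rule is one sentence: "Patients with no retreatment will be censored at the last visit". It makes no exception by reason for leaving, and no sensitivity analysis is described. Protocol 3.5 foresees the relevant case: "A subject may discontinue participation in the study at any time for any reason (e.g. lack of efficacy, withdrawal of consent, AE".

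On strata, the protocol synopsis states: "Randomisation will be stratified by aetiology of NDO (SCI or MS) and also by previous intradetrusor botulinum toxin type A (BTX-A) usage". The SAP prose names the stratification variables for the primary MMRM (7.6.3), the ANCOVA (7.6.4.2), and the GLMM and logistic models (7.6.5). For the logistic model it reads: "The model will include treatment group, and stratification variables". The log-rank prose names none. Section 7.6.6.4 then announces "The SAS codes of survival analysis for reference are below", and that code is blacked out.

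SAP 7.6.6 classes every secondary endpoint outside the hierarchy as exploratory, and this is one of them.

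**The concern.** Efficacy against placebo, including duration of effect, is a stated secondary objective (Protocol 2.2), and this comparison is its only formal test. Three things in the readable text are weaker than they need to be.

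- **Stratification is unstated.** A reader cannot tell whether the test respects the randomisation strata. If they are prognostic for time to retreatment, an unstratified log-rank test gives up some power.
- **There is no treatment-effect estimate.** The result is a p-value beside separate within-arm percentiles. The MMRM and ANCOVA report a difference with a 95% CI, and the logistic analyses report an odds ratio with a 95% CI.
- **Censoring ignores the reason for leaving.** Kaplan-Meier assumes that censored subjects would have gone on like those still followed. A subject who leaves because the effect has gone, or never came, probably would not. The duration reported for that arm is then too long.

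**Working it through.** **1. The plan's own figures.** The only sizing in the documents is for the primary endpoint (SAP 2.3): difference 9, SD 20, two-sided alpha 0.025, power 80%. The normal approximation gives n = 2 × (2.241 + 0.842)² × (20/9)² ≈ 94 per group. With the t distribution, 96 per group has 80.4% power, so the stated 96 reproduces. No hazard ratio, event count, power or lack-of-efficacy withdrawal rate is given for time between treatments. Everything below therefore rests on assumptions and is illustrative.

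**2. What stratifying is worth.** Inputs from the documents: 110 per arm with placebo sequences pooled, a 2 × 2 stratification, no retreatment before week 12, follow-up to week 104, two-sided 5%. Assumptions: four equal strata, exponential times after week 12 (placebo median 22 weeks in the reference stratum), 10% random loss. The statistic is Z = Σ(O − E)/√ΣV, computed over the whole sample (unstratified) or within strata and summed (stratified). With 4,000 runs per setting, simulation error is about 0.7 points where power is 70%.

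Power, unstratified → stratified (%), by the hazard ratio of each stratification factor:

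| Treatment HR | factor HR 1 | 1.25 | 1.5 | 2 |
|---|---|---|---|---|
| 0.60 | 96.0 → 94.7 | 95.2 → 94.7 | 94.0 → 94.7 | 91.4 → 95.3 |
| 0.65 | 87.1 → 85.7 | 86.3 → 86.6 | 84.3 → 87.0 | 78.2 → 85.9 |
| 0.70 | 71.9 → 70.1 | 72.1 → 71.6 | 69.0 → 72.5 | 60.8 → 71.5 |

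Stratifying costs 1 to 2 points if the factors do nothing and makes no real difference at 1.25. It gains 0.7 to 3.5 points at 1.5, and about 4 to 11 only if each factor doubles the hazard.

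Under no treatment effect, with factor HRs of 1, 1.5 and 2 (6,000 runs each, simulation error about 0.3 points), the unstratified test rejected in 5.0%, 4.2% and 3.6% of runs. The stratified test rejected in 4.8%, 5.3% and 5.8%. The unstratified test is therefore valid, and conservative when the strata matter.

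**3. What the censoring rule does to the medians.** With a true median of m weeks, the time to retreatment is T = 12 + an exponential with median m − 12. A fraction of subjects leaves for lack of efficacy at 12 + (T − 12) × U, with U uniform on 0 to 1. They are either censored there (the SAP rule) or counted as events there. Medians come from S(t) = ∏(1 − d/n), with 200,000 subjects per arm. Selected settings, in weeks; gaps were taken before rounding:

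| True medians, placebo / active | Leaving, placebo / active | Placebo: censored / event | Active: censored / event | Gap: censored / event | Change in gap |
|---|---|---|---|---|---|
| 20 / 36 | 2% / 2% | 20.1 / 19.9 | 36.3 / 35.6 | 16.2 / 15.7 | +0.5 |
| 20 / 36 | 10% / 5% | 20.6 / 19.4 | 36.9 / 35.2 | 16.4 / 15.8 | +0.6 |
| 24 / 36 | 15% / 5% | 25.3 / 22.6 | 36.8 / 35.1 | 11.5 / 12.4 | −0.9 |
| 20 / 48 | 10% / 5% | 20.6 / 19.4 | 49.5 / 46.9 | 29.0 / 27.5 | +1.5 |

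Over all twelve settings run (placebo 2% to 15%, active 2% to 5%), censoring gave a median 0.2 to 2.7 weeks longer than counting the leavers as events. Against the simulated true median, censoring was 0.1 to 1.3 weeks too long, and counting as events was 0.1 to 1.4 weeks too short. In this model the two rules bracket the truth. The gap between arms changed by −0.9 to +1.5 weeks.

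The model has no leavers before week 12. Such subjects leave the risk set before an event is possible, and matter only if their later course would have differed from that of subjects who stay.

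**The case against.** A reader might infer that the test is unstratified and ignores the randomisation. The documents do not show that. The code that would carry a strata statement is redacted, and redacted text is not missing from the plan. Nor is there a conflict with the protocol: section 9.4.5 commits the two factors to the primary model and promises only Kaplan-Meier and log-rank methods for time-to-event data. This stands in full. The fair statement is that the readable prose is silent where the prose for other models is not.

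A reader might also infer lost power or a failed design. No power is claimed for this endpoint, the unstratified test is valid, and the gain from stratifying depends on unknown strata effects. Protocol 1.6 suggests that response to BTX-A does not vary much on retreatment, which hints that prior use may be weakly prognostic. This also stands.

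On censoring, the strongest reply is definitional. The endpoint is the time between two administrations (Protocol Table 19), so a subject never re-administered has no event, and counting withdrawal as one creates a different, composite endpoint. That defeats any call to replace the main rule. It does not defeat a sensitivity analysis.

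Active retreatment from 12 weeks (Protocol 1.7) gives a dissatisfied subject a reason to stay, so such withdrawals may be few. SAP 7.2 tabulates reasons for withdrawal by group and cycle, so an imbalance would be seen. It would be seen, but its effect on the medians would not be measured.

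Finally, the within-arm percentiles carry CIs, so the size of effect is not wholly absent. Even so, no between-arm estimate with an interval is described.

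**Conclusion.** The point holds as a low-cost improvement to an exploratory analysis. Three statements are supported: the readable text leaves stratification unstated, it gives no between-arm estimate, and it censors lack-of-efficacy leavers with no sensitivity analysis.

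The censoring lengthens the Kaplan-Meier duration within an arm only if those leavers would have needed retreatment sooner than the subjects who stay. Its size, roughly 0.2 to 3 weeks between the two ways of handling them, rests entirely on assumed withdrawal rates and medians.

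It would be tempting to conclude that the plan overstates duration relative to placebo. The documents do not support that. In the settings run the between-arm gap moved either way, and it narrowed most where many more placebo subjects left. No controlled alpha depends on this test, and no stated power is missed.

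**What to change.** In SAP 7.6.6.4, for the double-blind placebo-controlled comparisons of each dose with placebo:

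- State that the log-rank test is stratified by aetiology of NDO and prior intradetrusor BTX-A use. If the redacted code already does this, say so in the prose.
- Report a stratified Cox hazard ratio with 95% CI beside the Kaplan-Meier percentiles.
- Keep the current censoring rule for the main analysis.
- Add a sensitivity analysis that counts withdrawal for lack of efficacy as an event at the withdrawal date, or as a competing event. Other withdrawals stay censored.

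No new data are needed: Protocol 4.4 already requires the reason for and date of withdrawal on the eCRF. The cost is a few lines of SAP text, a little programming, and about 1 to 2 points of power if the strata are not prognostic.

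In the same edit, reconcile SAP 7.6.6, which confines statistical comparisons to the placebo-controlled cycle, with 7.6.6.4, which also runs log-rank tests in the Dysport cycles.

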7.6.7 Subgroup Analysis

- 1) For the primary endpoint (DBPC Cycle at Week 6), the following baseline subgroups will be assessed for the mITT population:
 - Aetiology of NDO (SCI or MS)
 - Prior intradetrusor BTX-A usage (BTX-A bladder naïve or BTX-A bladder non-naïve)

-
- Age groups (≥ 18 to ≤ 40 , >40 to ≤ 65 , > 65 years)
 - Sex (Male or Female)
 - Concomitant use of anticholinergics and/or beta-3 agonists (Yes or No)
- 2) For the secondary efficacy endpoints included in the hierarchical analysis (DBPC Cycle at Week 6), the following baseline subgroup will be assessed for the mITT population:
- Aetiology of NDO (SCI or MS)

For 1) and 2) descriptive statistics and statistical analysis will be performed for each subgroup as detailed in section [7.6.3](#) and 7.6.5, with subgroup*treat interaction included in the analysis model. The subgroup analysis will be omitted if the subcategories have fewer than 30 subjects counts.

For 1), the treatment differences and 95% CI will be presented for each subgroup (e.g. Aetiology of NDO: SCI and MS) on a forest plot.

7.7 Safety

All safety data will be included in the subject data listings. Summary tables will be based upon the safety population.

7.7.1 Adverse Events

All AEs will be coded by Sponsor using MedDRA v21.0 (March 2018); (the latest version if updated during the study), and will be classified by MedDRA preferred term and system organ class.

A TEAE is defined as any AE with start date/and time at or after the date/and time of the first dose of IMP, or any AE with start date/and time prior to the date/and time of the first dose of IMP whose intensity worsens at or after the date/time of the first dose of IMP. The Pre-treatment AE is defined as any AE with start date/and time prior to the first dose of IMP administration in DBPC Cycle, and after the date of informed consent.

All TEAEs will be assigned to either DBPC Cycle and/or Dysport Cycle X based on the start date and time, or intensity increase date. For example, for presentation of TEAEs by Dysport Cycle, if the start time/intensity increase time of TEAE is at or after the time of treatment administration of Dysport Cycle X, Day 1 and prior to the time of treatment administration of Dysport Cycle X+1, Day 1, the TEAEs will be assigned to Dysport Cycle X.

In this study, an AESI is for Dysport is TEAEs that suggest a possible remote spread of effect of the toxin or events suggestive of hypersensitivity like reactions. TEAEs due to possible remote spread of the effects of Dysport will be identified using the list of MedDRA PTs compatible with the mechanism of action of BTX-A and based on the recommendations from the Committee for Medicinal Products for Human Use (CHMP) and the Food and Drug Administration (FDA). TEAEs potentially representing hypersensitivity reactions will be identified using the Standardised MedDRA Query (SMQ) (narrow search query) for hypersensitivity reactions. A list of MedDRA preferred terms, used to identify any potential AESI, is provided in Appendix VI.

Statistical Analysis Plan

Version: Final v2.0

September-2018

Ipsen Protocol No. D-FR-52120-222

000000146259

Date of Issue: 21-

Covance Study ID:

All TEAEs identified using the search strategy described above will be medically evaluated during the study, before the database lock and unblinding, by the sponsor to identify events which could possibly represent ‘remote spread of effect of toxin’, or which are suggestive of ‘hypersensitivity reactions’ due to study treatment administration. Cases will be excluded if they are confounded by presence of alternative clinical etiologies (medical history, concomitant medication or diagnosis which could account for the symptoms); if they are considered to be local effects instead of distant spread as judged by the site of injection; the time period between the last study treatment administration and event onset is not in accordance with the expected mechanism of action; or due to insufficient information/evidence to make an assessment.

In the TFLs, only the final list of AESIs confirmed by the sponsor as “a possible remote spread event” or “hypersensitivity reactions” will be taken into account.

All AEs (with TEAEs flagged) reported during the study will be presented in a listing which will be sorted by treatment group in the respective assigned treatment cycle for that AE, subject ID, AE start date and time, primary system organ class (SOC), preferred term (PT), and verbatim text. The treatment cycle where the TEAE onset or intensity increased will be presented in the listing as well. Separate listings of all TEAEs, serious TEAEs, IMP-related TEAEs, TEAE of special interest, other protocol defined TEAEs, TEAEs leading to early withdrawal and TEAEs leading to death reported during the study will also be presented.

Overview tables will be produced for DBPC Cycle, Dysport Cycles and overall for the number and percentage of subjects with at least one of the following TEAEs, where subjects with more than one TEAE in a particular category are counted only once in that category. The number of TEAE occurrences will be provided as well. Note that for TEAEs that could only occur in the MS population (e.g. MS exacerbation), the denominator for the percentage calculation will relate to the number of MS patients; these TEAEs will be identified in the tables.

- any TEAE
 - intensity of TEAE (mild, moderate, severe)
 - Any IMP related TEAE
 - Any TEAE leading to withdrawal
- any serious TEAE
 - any IMP related serious TEAE
 - any serious TEAE leading to withdrawal
- any TEAE of special interest by type of AESI
 - any AESI leading to withdrawal
 - any serious AESI
- any UTI TEAEs
 - UTI TEAEs leading to withdrawal
 - serious UTI TEAEs
- TEAE leading to death

In view of the anticipated difference in duration of the Dysport and placebo treatment cycles, this overview table will also be provided including only TEAEs occurring any time after first dose of IMP until up to 12 weeks after first IMP treatment administration.

A similar overview table will be produced for the number and percentage of subjects with at least one of the following events occurred pre-treatment for randomised subjects. The number of occurrences of the following events will be presented as well.

- any AE
 - Intensity of AE (mild, moderate, severe)
- any SAE
 - any SAEs leading to withdrawal
- AE leading to death

TEAEs will be summarised overall, for DPBC cycle, and Dysport Cycles with the number and percentage of subjects with TEAEs presented by primary SOC and PT. In addition, this table will be provided including only TEAEs occurring up to 12 weeks after first IMP treatment administration. This will also be summarised by aetiology of NDO.

The same summaries for overall, for DBPC Cycle, and Dysport Cycles with the number and percentage of subjects with TEAEs presented by primary SOC and PT will be presented for serious TEAEs, IMP-related TEAEs, TEAEs leading to withdrawal, TEAEs of special interest, and other protocol defined TEAEs. TEAEs with PTs observed in $\geq 1\%$, $\geq 2\%$, and $\geq 5\%$ of subjects and IMP-related TEAEs with PTs observed in $\geq 1\%$, $\geq 2\%$, and $\geq 5\%$ of subjects will be summarised as well.

Additionally, TEAEs will be tabulated by decreasing overall PT frequency and intensity in each SOC and PT category.

The above will also be presented for SAEs.

